5.8.2 Vital Signs

Vital signs will be measured at all visits indicated in the schedule of assessments (Table 10) and documented in the medical record. Measurements to be reported are temperature in Celsius or Fahrenheit, pulse (beats per minute), respiratory rate (breaths per minute), oxygen saturation, and blood pressure.

Vital sign measurements will be collected within 30 minutes prior to study drug administration, and every 30 (\pm 10) minutes during the 60-minute AGEN1884 infusion, including at the end of the 15-minute flush of the infusion line (\pm 15 minutes). This would equate to 4 sets of vitals over the course of a 60-minute infusion and flush, including the pre-administration vitals. A final set of vitals will be collected 1 hour (\pm 15 minutes) following the flush of the infusion line, unless otherwise indicated.

Because AGEN1884 is administered based on subject body weight, weight will be collected before each dose of AGEN1884 to confirm the administered dose. The subject's weight at the Week 1 (Cycle 1, Day 1) visit should be used for dosing calculations unless there is a >10% change in body weight. Dose adjustments for each cycle are only needed for a >10% change in weight.

5.8.3 12-Lead Electrocardiogram

A 12-lead ECG will be recorded as indicated in the schedule of assessments (Table 10). The corrected QT (QTc) interval will be calculated using Fridericia's formula.

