8.6.1 Drug Exposure

Overall drug exposure will be summarized in Safety Analysis Set by the following parameters:

- Duration of treatment (week), calculated as: (last dose date first dose date + 1)/7
- Number of treatment infusions received
- Total cumulative dose (mg), defined as the sum of the actual doses (mg) taken
- Dose compliance, defined as percentage of actual dose taken relative to planned dose
- Planned/actual dose intensity for the first 4 cycles, defined as total planned or actual dose from the first 4 cycles (mg) divided by actual duration of the first 4 cycles (weeks)

Note: if patients permanently withdraw from the treatment before Cycle 4 due to reasons other than disease progression or death, the remaining cycles will be calculated with planned length, i.e., 3 weeks, and zero dose. If patients withdraw from the treatment due to disease progression or death, the number of cycles actually completed will be used.

- Number of doses with infusion related reactions (as reported on drug administration eCRFs)
- Number of subjects with at least one infusion related reaction
- Number of subjects with any dose interrupted/not completed
- Number of doses interrupted/not completed
- Occurrences and number of actual doses exceeding adjusted planned dose by more than 5% (adjusting for up to 10 % weight loss.)

Per pharmacy manual, no adjustment in dose was required for body weight changes within 10%, therefore dose exceeding planned dose by > 5% will be interpreted as any dose 5% greater than the highest daily dose prescribed by the clinical trial protocol, after accounting for up to 10% changes due to decrease in body weight. Adjusted planned dose is calculated by multiplying prescribed dose level by adjusted weight W_{adj} . Denoting by W_0 and W_{adj} the baseline and the most recent weights, adjusted weight is: $W_{adj} = W$ for $W \ge W_0$ and $W_{adj} = \min(W_0, 1.1 \times W)$ for $W < W_0$.

Missing weight measurements in drug exposure analysis will be imputed by last observation carried forward, multiple measurements for the same timepoint will be averaged.

Confidential Page 20 of 30

Details of study treatment exposure will be listed for Safety Analysis Set.

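### The SAP's excess-dose count keeps its weight-loss allowance past 10%, where the protocol stops accepting an unadjusted dose

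*SAP*

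**What the plan says.** Protocol 5.8.2 (Vital Signs) has weight collected before each dose and sets the dosing basis: "The subject's weight at the Week 1 (Cycle 1, Day 1) visit should be used for dosing calculations unless there is a >10% change in" that weight. It adds: "Dose adjustments for each cycle are only needed for a >10% change in weight". Protocol 4.4.1 permits no dose reductions or escalations, so body weight is the only planned reason for the milligram dose to change.

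SAP 8.6.1 (Drug Exposure) plans a count of actual doses more than 5% above an adjusted planned dose. It gives its reason: "Per pharmacy manual, no adjustment in dose was required for body weight changes within 10" per cent. It then interprets an excess as "any dose 5% greater than the highest daily dose prescribed by the clinical trial protocol, after accounting for up to 10% changes", limited to decreases in weight. The calculation follows: "Adjusted planned dose is calculated by multiplying prescribed dose level by adjusted weight". With W0 the baseline weight and W the most recent weight, adjusted weight (W_adj) is W when W ≥ W0, and min(W0, 1.1 × W) when W < W0.

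**The concern.** The reason given for the allowance covers weight changes within 10% only. The formula has no corresponding limit: 1.1 × W applies however far weight has fallen. Just beyond a 10% loss the protocol no longer supports dosing on the Cycle 1 Day 1 weight, but the count still credits the subject with 10% extra weight and then adds the 5% tolerance. A site that misses the adjustment would be reported as not exceeding plan.

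What is at stake is the accuracy of one exposure summary for a weight-dosed drug in a study whose primary endpoints include safety. The count would understate excess doses in the range where the protocol's adjustment rule first applies.

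**Working it through.** The plan states no figure to reproduce, so this is algebra on the SAP formula.

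**Inputs**
- Dosing weight W0, kept until the change exceeds 10%: Protocol 5.8.2.
- W_adj = min(W0, 1.1 × W) for W < W0, and a flag when actual dose > 1.05 × dose level × W_adj: SAP 8.6.1.
- Dose level 1 mg/kg in Phase 2: Protocol 3.1. It cancels from every ratio below.
- Assumption: the SAP's baseline weight and the Cycle 1 Day 1 dosing weight are the same.

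**Flag condition for an unadjusted dose.** The dose given is level × W0, so it is flagged when W0 > 1.05 × min(W0, 1.1 × W).

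1. While 1.1 × W ≥ W0, that is W ≥ W0/1.1 = 0.9091 × W0 (loss up to 9.09%), W_adj = W0. The ratio is 1 and there is no flag.
2. Beyond that, W_adj = 1.1 × W. A flag needs W0 > 1.05 × 1.1 × W = 1.155 × W, so W < 0.8658 × W0, a loss above 13.42%.

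| Loss from W0 | W_adj / W0 | Unadjusted dose ÷ SAP adjusted planned dose | Flagged by SAP | Unadjusted dose ÷ current-weight dose |
|---|---|---|---|---|
| 9% | 1.0000 | 1.0000 | no | 1.0989 |
| 10% | 0.9900 | 1.0101 | no | 1.1111 |
| 11% | 0.9790 | 1.0215 | no | 1.1236 |
| 12% | 0.9680 | 1.0331 | no | 1.1364 |
| 13% | 0.9570 | 1.0449 | no | 1.1494 |
| 13.42% | 0.9524 | 1.0500 | boundary | 1.1550 |
| 14% | 0.9460 | 1.0571 | yes | 1.1628 |

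The uncounted band runs from just above 10% (protocol trigger) to 13.42% (SAP formula). Doses in it are 1/0.9 − 1 = 11.1% to 15.5% above the current-weight dose.

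**Example (assumed weights, 1 mg/kg).** Baseline 80 kg, now 70 kg (loss 12.5%), 80 mg given. W_adj = min(80, 77) = 77 kg and the limit is 1.05 × 77 = 80.85 mg, so 80 mg is not flagged, although 80/70 − 1 = 14.3%. Using 70 kg as the reference, the limit is 1.05 × 70 = 73.5 mg and 80 mg is flagged.

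**The case against.** The best defence is that accounting for up to 10% can describe a cap on the credit instead of a cut-off. On that reading min(W0, 1.1 × W) does what it says. The wording allows this, but it does not rescue the result. At a first loss above 10%, an unadjusted dose more than 11% above the current-weight dose is still reported as within 5% of plan, and the reason the SAP gives for the credit no longer applies.

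A second defence has more force. Keeping 1.1 × W suits a subject whose dose was re-based and who then lost a little more. Take 80 kg falling to 70 kg, re-based to 70 mg, then 64 kg. The further loss is 6/70 = 8.6%. The SAP limit is 1.05 × min(80, 70.4) = 73.9 mg, so 70 mg is not flagged. A simple cut-off setting W_adj = W below 0.9 × W0 gives 1.05 × 64 = 67.2 mg and flags a dose that complies if change is measured from the last dosing weight. Protocol 5.8.2 does not say which weight later changes are measured from, and the pharmacy manual is not among the documents. This part of the objection stands, and it shapes the fix.

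Three stronger readings might be inferred and are not supported:
- That the formula gives a full 10% at every loss. The cap at W0 keeps the allowance below 10% for losses under 9.09%.
- That it wrongly flags compliant doses between 9.09% and 10% loss. At 10% the limit is 1.05 × 0.99 × W0 = 1.0395 × W0, so a W0 dose passes.
- That such doses vanish from the report. SAP 8.6.1 also plans dose compliance, cumulative dose, dose intensity and an exposure listing; SAP 8.4 plans deviation review and a listing of all deviations; SAP 8.6.5 lists weight by visit.

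**Conclusion.** The point holds as a mismatch between the SAP formula and the 10% rule used to justify it. For a dose left on the Cycle 1 Day 1 weight after a first loss of more than 10% and up to 13.4%, the count records no excess, although the dose is 11.1% to 15.5% above the current-weight dose. Both edges of the band are exact, given that baseline and Cycle 1 Day 1 weight coincide and that the pharmacy manual uses the same 10% trigger as the protocol.

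The matter is minor. The documents give no rate of weight loss or of missed adjustments, so neither the number of subjects affected nor any claim that this is a common error can be derived. The count is descriptive and no endpoint or decision rule depends on it. The reason to correct it is that the summary would be wrong by its own definition, and the weights needed are already collected.

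**What to change.** Reconcile SAP 8.6.1 with Protocol 5.8.2 by basing the count on the dosing reference weight:

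- W_ref = W0 until a recorded weight differs from W_ref by more than 10%; W_ref then becomes that weight.
- W_adj = max(W, W_ref).
- Keep the 5% tolerance.

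State in the SAP whether later changes are measured from Cycle 1 Day 1 or from the last re-based weight, in line with the protocol and pharmacy manual. The derivation above assumes the re-based weight and needs altering if the answer is Cycle 1 Day 1. This concerns the analysis count only; the dosing rule itself is for those documents to settle.

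Check on the two examples: 80 kg to 70 kg with 80 mg given has W_adj = 70 and limit 73.5 mg, so it is flagged. Then 64 kg with 70 mg given has W_adj = max(64, 70) = 70 and limit 73.5 mg, so it is not flagged.

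The cost is a few more lines of derivation, because W_ref must be carried across visits, and possibly more flagged doses. The limit also steps at the 10% boundary: with W0 = 80 kg it falls from 84.0 mg at 72.0 kg to 75.5 mg at 71.9 kg. A small weight difference, or the averaging of repeat weights that SAP 8.6.1 plans, can therefore decide a flag. Listing W, W_ref and the limit beside each flagged dose would make such cases visible.

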8.6.2 Adverse Events

Adverse events (AEs) will be coded using MedDRA version 22.1 and will be classified by SOC and PT.

Severity of AEs will be assessed by investigators according to the National Cancer Institute (NCI) Common Terminology Criteria for Adverse Events (CTCAE) Version 5, and AEs will be classified by investigators as either related or not related to the study drug. If the AE is reported as "Possible Related", "Probable Related", or "Highly Probable/Definite Related" in the eCRF, it will be considered as related; if it is reported as "Unrelated" or "Unlikely Related", it will be considered as unrelated.

Pre-existing conditions are those that started before and continued after signing of informed consent. Prior AEs (not treatment-emergent) are those occurring after the subject signed the informed consent and before the administration of the first dose of study treatment. Immune-related AEs will be evaluated in the extended on-treatment period to account for late toxicities. A separate listing will be provided for AEs incurred after on-treatment period.

Unless otherwise specified, TEAEs are AEs with onset during or after administration of first dose, or the worsening of a pre-existing condition during the on-treatment period. Immune-related AEs will be considered TEAEs during the extended on-treatment period. In a sensitivity analysis, TEAEs will be defined as AEs with onset during or after administration of first dose, or the worsening of a pre-existing condition during the extended on-treatment period. A separate listing will be provided of all AEs with onset date, or worsening date between end of "On-treatment period" (35 days) and end of "Extended on-treatment period" (90 days).

Any missing onset date, causality, or severity must be queried for resolution. Unresolved/missing causality and severity will be handled according to the following rules:

- An unresolved causality will be considered treatment-related
- An unresolved severity will be identified as an unknown severity

AEs with partial dates will be considered TEAEs unless the AE can unequivocally be determined as not treatment-emergent.

The following AEs are considered as AEs of special interest (AESIs):

- Infusion-related reactions per definition in NCI-CTCAE version 5 specification (per investigator assessment)
- Any elevated liver function test by investigators
- Any AE suspected to be immune-mediated (i.e. an irAE) by investigators
- Other AEs of special interest determined by investigators

Unless otherwise stated, the number of subjects with an event (subject-wise) and the number of events (event-wise) will be provided for each summary.

Immune-related AEs will be tabulated using investigator-reported irAEs.

Confidential Page 21 of 30

Agenus Inc. Statistical Analysis Plan for Study C-500-01 Phase 2

Infusion related AEs will be tabulated using infusion-related reactions as reported by the investigators.

The following summaries by either SOC and PT or by PT and by severity grade will be provided. Summaries will be sorted by decreasing incidence of PT (within SOC, if applicable).

- TEAEs by SOC and PT, and by PT
- TEAEs by relationship to study drug, severity grade, SOC, and PT
- Drug-related TEAEs by SOC and PT, and by PT
- TEAEs leading to permanent treatment discontinuation by PT
- TEAEs leading to death by PT
- Drug-related TEAEs leading to permanent treatment discontinuation by PT
- Drug-related TEAEs leading to death by PT
- Serious TEAEs by SOC and PT, and by PT
- Serious TEAEs by relationship to study drug and severity grade, by SOC and PT
- Drug related serious TEAEs by SOC and PT, and by PT
- irAEs by SOC and PT, and by PT
- irAEs by severity grade, SOC, and PT
- Infusion-related TEAEs by SOC and PT, and by PT
- Infusion-related TEAEs by severity grade, SOC, and PT
- Laboratory abnormalities worsening (in at least one on-study measurement, relative to baseline) by NCI-CTCAE version 5 criteria.
- Alanine aminotransferase (ALT), aspartate aminotransferase (AST), or bilirubin normal at baseline but with elevations $\geq 2 \times \text{upper limit of normal (ULN)}$

The overall summary of TEAEs will be reported by age (age < 55 vs age \geq 55, age < 65 vs age \geq 65, and age < 75 vs age \geq 75), by race group including at least 5 subjects (groups with < 5 subjects will be reported summarily as "Other"), by normal vs abnormal creatinine and bilirubin levels at baseline, and by drug manufacturing process. Subgroup analyses will be provided for HCC patients, non-HCC and PD-1/PD-L1 refractory patients, and non-HCC and PD-1/PD-L1 naïve patients.

In addition, the overall summary of AE incidence per month of drug exposure will be presented. Such a summary will report #patients/(total time of exposure in months) and #AEs/(total time of exposure in months.)

The analysis of irAEs in the above summaries will be performed using data as reported by investigators (the primary analysis). In addition, as an exploratory analysis, TEAEs using sponsor's definition of irAEs, will be summarized. If an AE falls within any of the cluster terms listed below, it will be considered as an irAE by sponsor's definition. For each irAE, the summary will include median time (and range) to onset, median duration (and range) in days of

Confidential Page 22 of 30

the first instance of such AE per patient. Finally, descriptive statistics will be provided for time of onset, cycle of onset, and cumulative dose at onset of first irAE by SOC.

If an SOC or PT was reported more than once for a subject, the subject would only be counted once in the incidence for that SOC or PT.

In tabulation by severity grade:

- For a given SOC, only the most severe SOC for each subject will be included
- For a given PT, only the most severe PT for each subject will be included

In addition, TEAEs (evaluated within the extended treatment period) will be reported for the following clusters of immune-mediated AEs: pneumonitis, colitis, diarrhea, hepatitis, hypothyroidism, hyperthyroidism, thyroiditis, hypophysitis, adrenal insufficiency, diabetes, nephritis, rash, pruritus, and other immune-related AEs. These clusters will be defined by the following MedDRA version 22.1 Preferred Terms:

- **Pneumonitis**: interstitial lung disease; pneumonitis; acute interstitial pneumonitis; immune-mediated pneumonitis
- Colitis: allergic colitis, autoimmune colitis, colitis, colitis erosive, colitis microscopic, enterocolitis hemorrhagic, eosinophilic colitis, necrotizing colitis, neutropenic colitis, enterocolitis, immune-mediated enterocolitis,
- Diarrhea: diarrhoea, diarrhoea hemorrhagic
- **Hepatitis:** acute hepatic failure, autoimmune hepatitis, hepatic failure, hepatitis, hepatitis acute, hepatoxicity, liver injury, hepatocellular injury, immune-mediated hepatitis, immune-mediated hepatic disorder, drug-induced liver injury
- **Hypothyroidism:** autoimmune hypothyroidism, hypothyroid goiter, hypothyroidism, immune-mediated hypothyroidism, myxoedema, thyroid atrophy
- **Hyperthyroidism**: Basedow's disease, hyperthyroidism, Marine Lenhart syndrome, primary hyperthyroidism, immune-mediated hyperthyroidism, secondary hyperthyroidism, tertiary hyperthyroidism, thyroid dermatopathy, thyroid crisis, thyrotoxic periodic paralysis, toxic goiter, toxic nodular goiter,
- **Thyroiditis**: autoimmune thyroiditis, thyroiditis, thyroid acute, thyroiditis chronic, thyroiditis fibrous chronic, thyroiditis subacute, immune-mediated thyroiditis
- Hypophysitis: hypophysitis, lymphocytic hypophysitis, hypopituitarism
- Adrenal insufficiency: Addison's disease, adrenal androgen deficiency, adrenal insufficiency, adrenal suppression, adrenocortical insufficiency acute, glucocorticoid deficiency, hypoaldosteronism, mineralocorticoid deficiency,
- **Diabetes** without prior history: type 1 diabetes mellitus, diabetes mellitus, latent autoimmune diabetes in adults, diabetic ketoacidosis, and hyperosmolar coma
- **Nephritis**: autoimmune nephritis, lupus nephritis, nephritis hemorrhagic, immune-mediated nephritis

Confidential Page 23 of 30

- Rash: pemphigoid, rash, rash erythematous, rash generalized, rash macular, rash maculopapular, rash pruritic, rash papular, immune-mediated dermatitis
- Pruritus: pruritus, pruritus allergic, pruritus generalized
- Other Immune-related AEs: myocarditis, immune-mediated myocarditis, uveitis, immune-mediated uveitis, iritis, vitiligo, psoriasis, myositis, immune-mediated myositis, rheumatoid arthritis, systemic inflammatory response syndrome, sarcoidosis, autoimmune disorder, meningitis, encephalitis, encephalitis autoimmune, immune-mediated encephalitis, encephalopathy, autoimmune encephalopathy, immune-mediated encephalopathy, Guillain-Barre syndrome, myasthenia gravis, demyelination, stomatitis, pancreatitis, autoimmune pancreatitis, pancreatitis acute, immune-mediated pancreatitis, immune-mediated gastritis, lichen planus, colitis ulcerative, Crohn's disease, inflammatory bowel disease, hemolytic anemia, immune-thrombocytopenia, immune thrombocytopenic purpura, aplastic anemia, bicytopenia, pancytopenia, immune-mediated pancytopenia

For each cluster, the analysis will summarize: the total incidence and number of all TEAEs included in the cluster and by severity grade, % of pts who received treatment with pituitary and hypothalamic hormones and analogues, with corticosteroids for systemic use, or with thyroid therapy (concomitant medications in, respectively, H01, H02, or H03 ATC2 groups indicated for AE and started following AE onset but no later than the date of AE resolution or 21 days from AE onset, whichever comes earlier), % leading to dose hold, % leading to drug discontinuation, % resolved, time to onset of first TEAE and duration of all TEAEs and TEAEs of grade ≥ 3.

The median duration of TEAE (in days) will be calculated using Kaplan Meier analysis for all patients and AE included in a cluster. Unresolved AEs or AEs with missing resolution information and date will be treated as censored data with the end of the extended on-treatment period as censoring date.

Death summary table will present reasons for deaths on treatment period, in survival follow-up, and overall.

Death details will also be listed (if applicable) including:

- Number of doses of study drug
- Number of cycles
- Age at death
- Study days relative to first dose date, calculated as (death date first dose date + 1)
- Number of days to death from last dose, calculated as (death date last dose date + 1)
- Precipitating AE (if death is an outcome of AE)
- Immune-related AE (if death is an outcome of irAE per investigator)
- Cause of deaths

The following listings will be provided in Safety Analysis Set:

Confidential Page 24 of 30

- All AEs (with TEAEs flagged)
- Related TEAEs
- Serious TEAEs
- TEAEs leading to treatment discontinuation
- TEAEs leading to death

Adverse events observed between signing the informed consent and first dose of study drug will be listed with negative study days.

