5.8.6.2 Recording and Reporting

5.8.6.2.1 Adverse Events

Subjects will be assessed for any AEs (non-serious or serious) from the date of consent until 90 days after the last study treatment. Any non-serious AEs identified during this time period will be followed until resolution or stabilization or only until the discontinuation from the study evaluation period if the event is not resolved at the conclusion of the study. The dates of onset and resolution for each AE will be recorded in the subject file. All AEs will be evaluated for duration, intensity, and attribution (relationship) to the investigational agent(s). All AEs (serious and non-serious) and laboratory abnormalities should be assessed for significance by the investigator, with consideration for the subject's overall medical history and concomitant medication profile.

If there is a change from baseline in a laboratory value, physical examination finding, vital sign, or medical finding, and the change is considered by the investigator to be clinically significant, the event must be recorded as an AE.

All AEs regardless of causality or seriousness must be recorded on the electronic case report form (eCRF). The frequency, grade, and nature of irAEs must be recorded.

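### As the TEAE definition is worded, a clinical AE that starts between consent and first dose and worsens after dosing is not treatment-emergent and may be missing from the TEAE tables.

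*SAP*

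**What the plan says.** SAP 8.6.2 sorts events by when they began.

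- Before consent: "Pre-existing conditions are those that started before and continued after signing of informed consent".
- Between consent and dosing: "Prior AEs (not treatment-emergent) are those occurring after the subject signed the informed consent and before the administration of the first dose" of study treatment.
- Treatment-emergent: "TEAEs are AEs with onset during or after administration of first dose, or the worsening of a pre-existing condition during the on-treatment period".

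The sensitivity definition keeps the same two routes and only lengthens the window: "or the worsening of a pre-existing condition during the extended on-treatment period". Under SAP 6.3 and 6.4 the two windows end 35 and 90 days after the last dose.

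The SAP 8.6.2 summaries of all, drug-related and serious events, and of events leading to discontinuation or death, are built on TEAEs. So are the immune-mediated cluster summaries. AEs from the consent-to-dose interval appear only in listings: the listing of all AEs with TEAEs flagged, and a listing with negative study days.

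The protocol does collect these events. Section 5.8.6.2.1 says: "Subjects will be assessed for any AEs (non-serious or serious) from the date of consent until 90 days after the last study treatment". Section 5.1.1 allows screening assessments up to 28 days before the first dose.

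**The concern.** The worsening route uses a term that the same section has just defined by reference to consent. Treatment-emergence, however, is meant to separate what happened before the first dose from what happened after it. An AE that begins in screening is present at baseline in the SAP's own sense, because SAP 6.1 takes baseline as the last value before the first dose. Yet if that AE gets worse on drug, the definition has no place for it.

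Safety and tolerability are a primary endpoint (SAP 4.4). A mild event that begins in screening and becomes severe, serious or treatment-ending on drug is the kind of event the TEAE tables exist to show. The definition also treats like cases differently: a grade 1 rash that starts the day before consent and reaches grade 3 on treatment counts, while the same rash starting the day after consent does not.

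**Working it through.** The plan gives no figure to reproduce. The check applies the SAP 8.6.2 definitions to each possible onset interval, assuming in each case that the event worsens within the on-treatment period.

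| Onset | Route 1: onset at or after first dose | Route 2: worsening of a pre-existing condition | Result |
|---|---|---|---|
| Before consent, continuing after it | No | Yes | TEAE |
| After consent, before first dose | No | No, because it did not start before consent | Prior AE, not a TEAE |
| At or after first dose | Yes | Not needed | TEAE |

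Only the middle row falls through. The sensitivity definition gives the same result, because changing the window does not change which conditions count as pre-existing.

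Next, whether another rule brings the middle row back in:

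1. **Immune-related events.** "Immune-related AEs will be considered TEAEs during the extended on-treatment period". This sets a longer window. It does not say what happens to an event whose onset precedes dosing, so it is not a clear rescue.
2. **Partial dates.** "AEs with partial dates will be considered TEAEs unless the AE can unequivocally be determined as not treatment-emergent". With a complete onset date before dosing, the rule does not apply. The contrast is awkward: under SAP 6.6, an AE with the day missing and its onset in the month of first dose is set to the first dose date and counted, while a fully dated screening AE that worsens is not.
3. **Recording rules.** Protocol 5.8.6.1.1 gives clinically significant worsening of a pre-existing condition as an example of an AE. Protocol 5.8.6.2.1 requires a clinically significant change from baseline to be recorded as an AE. If the site opens a new record with a post-dose onset date, route 1 captures it. Neither section requires a new record or a new onset date for an AE that is already open. SAP 8.6.2 itself refers to a worsening date alongside an onset date, which suggests that worsening can be tracked without a new onset.
4. **Laboratory summaries.** SAP 8.6.2 tabulates laboratory worsening from baseline, and SAP 8.6.4 gives shift tables from baseline grade to worst grade. Neither depends on TEAE status, so the gap concerns mainly clinical AEs.

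**Size.** Neither document gives a rate of screening AEs or of later worsening, so no count of affected events can be derived. What follows from the planned numbers (SAP 3.2) is the effect of one omitted subject on one table row:

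- 60 subjects in Phase 2: 1/60 = 1.7 percentage points.
- 40 non-HCC subjects: 1/40 = 2.5 percentage points.
- 20 HCC subjects: 1/20 = 5.0 percentage points.

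**The case against.** The strongest reply is that exclusion is not certain. The protocol requires clinically significant change from baseline to be recorded, and a site may well enter the worsened event as a new AE dated after dosing; route 1 then counts it. The SAP was prepared from a case report form (SAP 2) that is not among the documents, and that form may settle how grade changes are captured. This stands, and it is why the point says the event may be missing. It does not close the gap, because the result would then depend on site practice or form design rather than on the stated definition.

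Three further replies limit the point.

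- A reader might infer that toxicity carried over from the recent PD-1/PD-L1 inhibitor is being missed. Toxicity present before consent is a pre-existing condition, and its worsening already counts. Exclusion criterion 8 also bars unresolved prior-therapy toxicity above grade 1, apart from grade 2 neuropathy and alopecia. The gap covers only events that newly start after consent, are present at dosing, worsen later and are not re-recorded.
- A reader might infer that such events vanish from all safety output. They remain in the listings, laboratory worsening is tabulated, and the investigator-reported irAE tables may include them, though the text is not explicit.
- A reader might infer that whole subjects drop out of the tables. A subject leaves the overall TEAE count only if no other event qualifies. Otherwise the loss is a preferred-term row or its grade, and the system organ class row if nothing else falls there.

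It is also fair to say that the analysis is descriptive: the sample size is not inferential, and the documents tie no test to TEAE status.

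**Conclusion.** The definitional gap is real on the text of SAP 8.6.2 and affects both TEAE definitions. A clinical AE with onset between consent and first dose that worsens after dosing is not a TEAE as written, and may be absent from the TEAE tables as a preferred-term or grade entry. This rests on two conditions: the onset date is complete, and the site does not enter the worsening as a new AE with a post-dose onset.

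The documents do not support a stronger claim that these events are certainly excluded, or that a stated number of subjects is lost. Any such number would rest on assumed rates of screening AEs and of later worsening. The gap looks like unintended drafting, since older conditions that worsen are counted and newer ones are not. It is still worth correcting, because a stated rule misclassifies events in tables that serve a primary endpoint and is at odds with the SAP's own pre-dose baseline.

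**What to change.** In both TEAE definitions in SAP 8.6.2, replace the reference to a pre-existing condition worsening with: *worsening, on or after the first dose and within the period, of any condition or AE present before the first dose (including AEs with onset between consent and first dose)*. Limit the not-treatment-emergent label to prior AEs that do not worsen after the first dose.

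The other two onset classes keep their present classification, and no protocol amendment is needed. The cost is a small update to the TEAE derivation. It relies on the worsening date that the SAP already refers to and that the existing clause already needs. Because SAP 8.6.2 reports events as well as subjects, the programming should count the worsening once where a site has also opened a new record for it.
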